8.3.1 Analyses at local study sites

8.3.1.1 Potential study candidates. Blood will be drawn from potential study candidates following diagnostic coronary angiography for rapid measurement of LDL-C levels ("baseline blood draw #1"). The LDL-C measurement will be used as an inclusion criterion to determine eligibility for enrollment (section 4.1 and 7.1.1).

8.3.1.2 Enrolled patients. Once enrollment is confirmed, blood will be drawn ("baseline blood draw #2") to measure following parameters: hematocrit, hemoglobin, RBC count, WBC count, platelets, plasma glucose, sodium, potassium, ALT, AST, ALP, total bilirubin, CK levels. CK peak after revascularization should be obtained every 8 hours to assess peak levels (clinically relevant in the setting of acute myocardial infarction). Blood draw will be performed from venous sheaths placed routinely in patients with acute myocardial infarction, so as to avoid multiple punctures pre-enrollment (status "potential study candidate") and post enrollment (status "enrolled patient"). The same parameters will be measured on scheduled visits at Weeks 4 and 52.

8.3.2 Analyses at central lab

Samples will be collected on day 1 (post enrollment, during "baseline blood draw #2" as described above), Weeks 4 and 52 in routine blood tubes, serum, heparin-coated and EDTA-coated plasma tubes of 10 ml vacutainers. The study site personnel will carry the samples to the local laboratory where samples will be centrifuged immediately, aliquoted and frozen at -80°C for subsequent analyses. Samples from all study sites will be transferred to a fully automated central biobank at the University Hospital in Bern. Samples will be destroyed after study end, i.e. latest five years after the last visit of the last patient has been completed.

The following blood samples will be collected: serum (4 aliquots of 500 μ L and 4 aliquots of 250 μ L), EDTA-Plasma (4 aliquots of 500 μ L and 4 aliquots of 250 μ L) and heparin-plasma (4 aliquots of 500 μ L and 4 aliquots of 250 μ L).

Following analyses will be performed (Table 2):

See Appendix 1 for early and late effects of Alirocumab on Apolipoproteins

Table 2. Planned biomarker analyses.

	Conjuentui	
Key biomarkers	 Cholesterol, LDL-C, HDL-C, non-HDL-C, triglycerides, Lp (a), Apo A1, Apo B, ratio Apo B/Apo A-1, Apo C-III, Lp(a) hs-CRP, hs-troponin T, NT-proBNP TNFa, IL1b, IL-6, MPO, cystatine, SIRT1, SIRT6 PCSK9 levels 	• Planned to be analysed in Bern and Zurich
Neutrophil extracellular trap (NET)	DNAase activity	Planned to be analysed in Vienna

A. Key biomarkers

Levels of measured biomarkers will be correlated with coronary percent atheroma volume progression/regression by IVUS, changes in lipid content by NIRS, and changes in macrophage accumulations by OCT between baseline (Day 1) and follow-up (Week 52).

As substantial noise in many biomarkers is expected at baseline due to the qualifying diagnosis of myocardial infarction (unlikely to reflect baseline properties of non-culprit coronary arteries), analysis will also focus on biomarker levels at Week 4 (steady-state condition). This will allow us to collect biomarker data in a quiescent baseline status after the qualifying event.

B. Neutrophil extracellular trap formation - DNase activity

The rationale for measuring markers of neutrophil extracellular trap (NET) formation and its counterpart, DNase activity is that endoluminal NET formation has emerged as a major component of acute atherothrombosis.⁵⁴ Surrogate markers of NET predict cardiovascular events. Oxidized LDL is a trigger for NET release.^{55,56} We hypothesize that specific reduction of oxidized LDL by means of alirocumab reduces neutrophil activation, NET burden and coronary plaque progression.

For the measurement of nucleosomes (DNA-histone complexes), an ELISA - cell death detection kit (Roche Diagnostics GmbH, Germany) will be used. Optical density (OD) values will be set in proportion to the internal positive control and expressed as arbitrary nucleosome units/ml (NU/ml). The intra-assay positive control equals 1000 NU/ml. For the measurement of MPO-DNA complexes, a mouse anti-human myeloperoxidase antibody (AbD Serotec) will be coated. Results will be given as expressed as arbitrary MPO-DNA units/ml (NU/ml) in proportion to the internal control. For the measurement of citrullinated histone 3, a mouse anti-human histone 3 antibody (Abcam) will be used. Results will be given as expressed as arbitrary citH3 units/ml (NU/ml) in proportion to the internal control. For the internal control. For detection of double stranded DNA (dsDNA) in patient plasma, we will employ a Quant-iT PicoGreen dsDNA Assay (Invitrogen, USA) on 96-well microplates. Fluorescence will be measured by a Varioskan Flash microplate reader (Thermo Scientific, USA) and normalized to the provided standard (1000 ng/ml). Endogenous DNase activity will be measured employing a DNase Activity Assay (Orgentec Diagnostika GmbH, Mainz, Germany).

This analysis has the following aims:

- To compare NET surrogate markers and NETosis at baseline and Week 52 following treatment with alirocumab vs. placebo
- To correlate data on NETs with changes in coronary plaque burden and composition

9. STUDY OUTCOMES

9.1 Primary Endpoint

• The primary endpoint is the change in percent atheroma volume (PAV) as determined by IVUS, between baseline and 52-week follow-up from matched regions of interest. This endpoint is used for the pre-specified sample size calculation.

Justification of primary endpoint selection

The selection of PAV as the primary endpoint is consistent with previous serial IVUS studies assessing plaque regression in response to statin treatment,^{10,11} as well as with the GLAGOV study assessing the effect of evolocumab on coronary atherosclerosis. Among different IVUS measures of disease burden, change in PAV (i.e. percentage of vessel wall volume occupied by atheroma) is recommended due to smaller variability compared with other endpoints that may be sensitive to pullback length differences.³³

Prespecified stratified analyses of the primary endpoint will be performed according to the following characteristics: age, gender, diabetes mellitus, vessel localization, statin use at baseline, LDL reduction throughout study period, baseline plaque burden, maxLCBI4mm at BL, hsCRP on treatment levels.

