2. STUDY OBJECTIVES

2.1 Primary objective

• To evaluate the effect of LDL-C lowering by means of the PCSK9 inhibitor alirocumab as compared with placebo on the change in percent atheroma volume (PAV) in non-infarct-related coronary arteries of patients who present with acute myocardial infarction, undergo percutaneous coronary intervention (PCI) in the infarct-related artery, and receive guideline-recommended high-intensity statin therapy.

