12. STATISTICAL CONSIDERATIONS

12.1 Pre-specified sample size calculation

12.1.1 Evidence of effect sizes on PAV. Previous serial IVUS studies assessing the effect of different statin doses on PAV by IVUS showed a dose-response relation between changes of PAV and doses of statin (and consequently, magnitude of LDL-C reduction). In the CAMELOT trial, a PAV increase of +1.3% was seen in placebo patients who received standard-of-care statin regimens.⁵⁸ Hong et al.⁵⁹ found that rosuvastatin 20mg resulted in -0.46% reduction of PAV at 11 months. Using a higher-dosed statin regimen, we recently reported a 43% reduction of LDL-C at 13 months with rosuvastatin

40mg and a PAV reduction of -0.90% at 13 months.³⁵ Consistently, a 53% LDL reduction and -0.98% PAV reduction at 24 months with rosuvastatin 40mg was reported in the ASTEROID trial,¹⁰ and a 44% LDL-C reduction and -1.23% PAV reduction was found in the SATURN trial at 24 months.¹¹ Of note, a sub-analysis of our data from the IBIS4 trial demonstrated that patients with more pronounced (above-median) LDL-C reduction had an average PAV reduction of -1.66 %, whereas in patients with less pronounced (below-median) LDL-C reduction the decrease of PAV was only -0.16%.³⁵ This finding indicates that differences in the magnitude of LDL-C reduction are associated with a difference of the order of $\pm 1.5\%$ in PAV change within a single cohort. Of note, the addition of ezetimibe to atorvastatin in the PRECISE-IVUS trial resulted in incremental LDL-C lowering and PAV reduction compared with treatment with atorvastatin alone, an effect that was most pronounced in patients with acute coronary syndromes (i.e., similar to patients in the present study) as compared with patients with stable coronary artery disease.⁶⁰

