12.1.2 Rationale for expected effect size in each treatment arm. In summary, the observed range of PAV change over 1-2 years is in the range -1.2% to +1.3% in previous statin trials, with highest-dose statin regimens consistently associated with a PAV reduction of the order -0.90% to -1.23%. Along this line, the addition of alirocumab to maximally tolerated statin doses resulted in an incremental LDL-C reduction by 29.8% as compared to patients treated with maximal tolerated statin doses plus ezetimibe, with the proportion of patients reaching the LDL-C target of 70 mg/dl (1.8 mmol/L) being 77% vs. 45.6% and the proportion of patients reaching the extremely low LDL-C target of 50 mg/dl (1.3 mmol/L) being 60.3% vs. 14.2%, respectively.²⁷ Given the substantial incremental LDL-C reduction with alirocumab on top of maximally tolerated statin doses, we consider that a reduction in PAV beyond -1.23% is possible and we assume an expected PAV reduction of -1.8% in the PCSK9 inhibitor arm after 1 year. For the placebo arm of the proposed study that will receive rosuvastatin 20mg, the results by Hong et al⁵⁹ provide a reasonable benchmark to assume a moderate expected PAV reduction of -0.5%.

12.1.3 Sample size calculation. This is a superiority trial powered on the primary endpoint, change in PAV from baseline to 52 weeks (12 months). We assume a PAV change of -0.5% in the placebo arm and -1.8% in the alirocumab arm, with a common standard deviation of 3.4% (as a consensus from SATURN¹¹: 3.0%, IBIS4³⁵: 3.4%, ASTEROID¹⁰: 4.0%) and an intraclass correlation coefficient of *ICC*=0.40 (estimated from IBIS4 data). Given that *m*=1.8 vessels per patients are expected to be analyzed, this gives a *design effect* of *D*=1.4 [design effect computed as D = 1+ICC(m-1)]. If dropout was ignored, a total sample size of 176 patients would be necessary to reach a statistical power of 80% at a two sided alpha level of α =5%. Anticipating a dropout rate of 25% at the 12 month imaging follow-up, a total of n=220 patients should be recruited (110 per arm). See Appendix 1 for adjusted sample size and statistics

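### Section 9.1 pre-specifies strata for the primary endpoint by two variables measured after randomisation, LDL-C reduction and on-treatment hsCRP, so arm comparisons within them are not protected by randomisation

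*Protocol*

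**What the plan says.** Section 9.1 states: "Prespecified stratified analyses of the primary endpoint will be performed according to the following characteristics". The list opens with age, gender, diabetes and vessel location and ends with "statin use at baseline, LDL reduction throughout study period, baseline plaque burden, maxLCBI4mm at BL, hsCRP on treatment levels". Nothing separates the on-treatment items from the baseline ones, and neither is called exploratory, associational or a mediation analysis.

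Four other places bear on this:
- Section 2.1 frames the primary objective around the mechanism: "To evaluate the effect of LDL-C lowering by means of the PCSK9 inhibitor alirocumab".
- Section 12.1.1 reports that within a single earlier cohort "patients with more pronounced (above-median) LDL-C reduction had an average PAV reduction of -1.66"%, against -0.16% in patients below the median.
- Section 8.3 schedules blood sampling at Day 1, Week 4 and Week 52. Section 6.1.3 starts injections at Week 0 and repeats them at Week 2, so Week 4 and Week 52 values are both on treatment.
- Section 9.2.2 makes change in hsCRP a secondary endpoint and separately plans associations between biomarkers and plaque change.

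**The concern.** A subgroup estimate of a treatment effect keeps the protection of randomisation only if the subgroup is fixed before treatment can influence membership. LDL-C reduction over the study is the main pharmacological effect of alirocumab. A split on it sorts patients partly by arm. In the low-reduction stratum it sets alirocumab patients who responded poorly or took little drug against ordinary placebo patients. In the high-reduction stratum it sets ordinary alirocumab patients against unusually responsive placebo patients. Because LDL-C reduction also predicts PAV change, these groups differ in expected outcome for reasons other than assignment.

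At stake is the reading of results that would carry the label of pre-specified analyses of the primary endpoint. A reader could conclude that alirocumab does little once LDL-C response is taken into account, when the true effect is the same in everyone.

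**Working it through.** The protocol gives no figure for the stratified analyses, so there is none to reproduce. The checks below size the imbalance and the distortion.

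**Inputs from the protocol.** Section 12.1.3: "We assume a PAV change of -0.5% in the placebo arm and -1.8% in the alirocumab arm", a difference of -1.3 points, "with a common standard deviation of 3.4"%. Section 4.4: 43% LDL-C reduction on rosuvastatin 20 mg. Table 1: 51% and 61% reductions in the two ODYSSEY trials. Section 5.3: 1:1 allocation.

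**Assumptions.** Median split; normal distributions with equal SD of 15-25 points; the statin and alirocumab reductions multiply.

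**1. Imbalance in previously untreated patients.**
- Alirocumab arm: 100 × (1 - 0.57 × 0.49) = 72.1% and 100 × (1 - 0.57 × 0.39) = 77.8%.
- Difference from 43%: Δ = 29.1 to 34.8 points.
- Smaller arm's share of each median stratum = Φ(-Δ/(2·SD)). Lowest: Φ(-34.8/30) = 12%. Highest: Φ(-29.1/50) = 28%.
- Overlap of the two distributions is twice that, 25% to 56%.

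**2. Imbalance in patients already on a statin.** If placebo patients do not change, Δ = 51 to 61 and overlap is 4% to 31%.

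**3. Cross-check on attained LDL-C.** Section 12.1.2 gives 77% vs 45.6% of patients reaching 70 mg/dL and 60.3% vs 14.2% reaching 50 mg/dL. In three bins (below 50, 50 to 70, above 70) the arms hold 0.603, 0.167, 0.230 and 0.142, 0.314, 0.544. Overlap = 0.142 + 0.167 + 0.230 = 54%. The comparator there was statin plus ezetimibe, so overlap against placebo should be lower.

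**4. Distortion of a constant -1.3 effect.** Take Δ = 29, SD = 20. The median lies Δ/2 = 14.5 points, or 0.725 SD, from each arm mean. With φ(0.725) = 0.307 and Φ(0.725) = 0.766, the mean standardised deviation in the upper stratum is 0.307/0.766 = 0.40 for alirocumab and 0.307/0.234 = 1.31 for placebo.
- *Full mediation through LDL-C:* the LDL-C contrast left in the stratum is 29 + 20 × (0.40 - 1.31) = 10.8 points. Effect = -1.3 × 10.8/29 = -0.49.
- *Full mediation plus a shared cause* (correlation 0.5 with LDL-C response, 0.5 PAV points per SD): -0.49 - 0.5 × 0.5 × (0.40 - 1.31) = -0.26.
- *LDL-C only a marker of a shared cause* (correlation 0.5, 1.0 PAV point per SD): -1.3 - 1.0 × 0.5 × (0.40 - 1.31) = -0.85.

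The lower stratum is symmetric. Simulation with 1,000,000 patients per scenario, Δ of 17 to 35 and SD of 15 to 25, gave about -0.5 under full mediation and -0.14 to -0.37 with the shared cause added. The marker-only case, run at Δ = 29 and SD = 20, gave -0.84 and -0.86.

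**5. Precision.** Assume the 25% loss of section 12.1.3 also applies to 294 patients: 294 × 0.75 ≈ 220, or 110 per median stratum. Take step 1's shares for all patients. The variance of a patient mean is 3.4² × [1 + 0.40 × 0.8]/1.8 = 8.48. The 95% half-width is 1.96 × √[8.48 × (1/n₁ + 1/n₂)]: 1.7 for 13 vs 97, 1.2 for 31 vs 79, and 1.1 for a balanced 55 vs 55. The protocol's printed design effect of 1.4 would widen each by about 3%.

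**6. hsCRP.** The protocol gives no alirocumab effect to use. For assumed on-treatment ratios of 1.0 to 0.7 and a log-SD of 1, overlap is 2Φ(ln(ratio)/2) = 100% to 86%.

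**The case against.** The best defence is that section 9.1 does not say the arms are compared within strata. It speaks of stratified analyses of the endpoint. Section 12.1.1 uses a similar split within one cohort as a response association, and sections 8.3.2 and 9.2.2 plan such associations. Models, cut-points and labels may sit in the statistical analysis plan or in Appendix 1, neither of which is shown. This stands in part: the within-stratum contrast is an inference. It is still the natural reading for a two-arm primary endpoint, especially as the same list holds ordinary subgroup factors, and the choice of factors is fixed in the protocol itself.

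A second defence is that section 8.3.2 treats Week 4 as a quiescent baseline because Day 1 biomarkers are disturbed by the infarction. The noise is real. Week 4 nevertheless follows two injections, so it is no baseline for a treatment-effect subgroup.

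A reader might also infer more than the documents support:
- *That the arms hardly overlap.* Overlap is 25-56% in previously untreated patients and about 54% on the attainment figures. Near-separation appears only in prior-statin patients with the largest effect and smallest SD.
- *That on-treatment hsCRP strata are certainly biased.* No alirocumab effect on hsCRP is stated.
- *That the loss can be given as one percentage.* It depends on the strength of a shared cause, which the protocol does not supply. Steps 4 and 5 show attenuation, not reversal.
- *That STEMI versus NSTEMI must be a subgroup because it is a randomisation stratum.* Nothing in the protocol requires that.
- *That section 12.1.2 repeats the problem.* Its statement that alirocumab "resulted in an incremental LDL-C reduction by 29.8"% is effect-size rationale against an ezetimibe comparator, not a subgroup plan.

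**Conclusion.** The point holds as a moderate issue. Two of the nine pre-specified factors are post-randomisation variables. For LDL-C reduction the protocol's own text makes it both a result of treatment and a correlate of outcome, so within-stratum arm differences would not estimate the randomised effect. A constant -1.3 would shrink to about -0.1 to -0.85, and the smaller arm would be roughly 12-28% of each median stratum in previously untreated patients. Those sizes rest on the assumed median split, SDs, multiplicative reductions and causal models; the direction is the same in every scenario tried. For hsCRP the flaw is possible but unquantified.

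A reader should not conclude that the main result is in doubt. Section 12.2 rests superiority on the overall comparison of the arms, and neither that analysis nor the sample size uses these strata.

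**What to change.** In section 9.1, limit treatment-effect subgroups to variables fixed before randomisation by removing LDL-C reduction over the study and on-treatment hsCRP. Day 1 LDL-C and Day 1 hsCRP may take their place. Randomisation then keeps allocation near 1:1 in each stratum, and a constant effect would be estimated as -1.3 in each.

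Report LDL-C reduction and on-treatment hsCRP only under section 9.2.2, as exploratory, non-randomised associations with PAV change, either within arm or with arm in the model.

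The cost is wording: both Day 1 values are already collected, and no visit, sample or patient is added. There are two drawbacks. Day 1 hsCRP is noisy because of the infarction (section 8.3.2). Day 1 LDL-C is partly tied to prior statin use, since section 4.1 sets different entry thresholds (70 and 125 mg/dL), so it overlaps with the baseline statin factor already listed.

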9.2 Secondary Endpoints9.2.1 Secondary imaging endpoints

Pre-specified secondary imaging endpoints are measures of change between baseline and 52-week (12-month) follow-up from the matched ROI:

- Change in lipid-core burden index (LCBI_{total}) as determined by NIRS, between baseline and 12-month follow-up from matched ROI
- Change in maximum LCBI in any 4-mm segment (maxLCBI_{4mm}) as determined by NIRS
- Change in minimal and fibrous mean cap thickness as determined by OCT
- Change in Average Angular Extension (AAE) of macrophages as determined by OCT, between baseline and 12-month follow-up from matched ROI.
- Change in normalized total atheroma volume (NTAV)

9.2.2 Secondary biomarker endpoints

- Change in LDL-cholesterol, hs-CRP, hs-TnT and NT-pro-BNP as well as lipid and inflammatory markers (**Table 2**) between baseline (Week 0), Week 4, and Week 52
- Association between levels of biomarkers and changes in plaque characteristics as described in the primary and secondary imaging endpoints

9.2.3 Secondary clinical endpoints

- Death
- Cardiac death

- Myocardial infarction
- Any coronary revascularization
- Stroke, transient ischemic attack

The definition of cardiac death includes any death due to immediate cardiac cause, procedure-related deaths, and death of unknown cause. The diagnosis of MI requires ischemic signs or symptoms and new pathological Q-waves in ≥ 2 contiguous electrocardiogram leads. In the absence of Q-waves, the diagnosis of MI is based on an elevation in CK to $\geq 2 \times$ upper limit of normal and an elevation of CK-MB or troponin to $\geq 3 \times$ upper limit of normal.

Any patient who develops a major adverse cardiac event during the follow-up period should be evaluated by the Investigator. Case Report Form for Event and data regarding any adverse events will be sent to the Clinical Event Committee. The Clinical Event Committee, consisting of cardiologists not participating in the trial, will review and adjudicate all major adverse cardiac events. The members of the Clinical Event Committee will be blinded to the patient's treatment allocation.

9.2.4 Secondary safety endpoints

• Adverse events (AEs), serious adverse events (SAEs), adverse events of special interest (AESIs), product complaints, laboratory data (refer to **Section 10** for details).

10. DEFINITION AND REPORTING OF ADVERSE EVENTS

10.1 Definitions of adverse events

An adverse event (AE) is any untoward medical occurrence or clinical investigation in a patient administered a pharmaceutical product and which does not necessarily have to have a causal relationship with this treatment.

10.2 Definitions serious adverse event

A serious adverse event (SAE) is any untoward medical occurrence that at any dose:

- Results in death, or
- Is life-threatening, or
- Requires inpatient hospitalization or prolongation of existing hospitalization, or
- Results in persistent or significant disability/incapacity, or
- Is a congenital anomaly/birth defect
- Is a medically important event

Medical and scientific judgment should be exercised in deciding whether expedited reporting is appropriate in other situations, such as important medical events that may not be immediately lifethreatening or result in death or hospitalization but may jeopardize the patient or may require medical or surgical intervention (i.e., specific measures or corrective treatment) to prevent one of the other outcomes listed in the definition above.

10.3 Definitions of suspected, unexpected, serious adverse reaction

An "unexpected" adverse drug reaction is an adverse reaction, the nature or severity of which is not consistent with the applicable product information (e.g. Investigator's Brochure for drugs that are not yet approved and Product Information for approved drugs, respectively).

The DSMB will evaluate any SAE that has been reported regarding seriousness, causality and expectedness. If the event is categorized as "possibly", "probably" or "definitively" related to the investigational product and is both serious and unexpected, it will be classified as a potential SUSAR. A potential SUSAR will require unblinding to determine a SUSAR. The DSMB will provide an overall assessment of benefit and harm given the observed rates of SAE at that time.

